### **7.12.4 Irritable Bowel Syndrome-Symptom Severity Scale (IBS-SSS)**

At each assessment of the IBS-SSS, the IBS-SSS Total score will be calculated. Descriptive statistics will be presented for the IBS-SSS Total score and each severity score. (See Section [9.12.4](#) for scale scoring)

## 8. CHANGES FROM ANALYSES PLANNED IN THE PROTOCOL

- a. For the key efficacy parameters Weekly Change from Baseline in Abdominal Pain and Weekly Change from Baseline in CSBM Frequency, the protocol states:

*Additional exploratory comparisons between the linaclotide doses (DR1, DR2) and linaclotide IR,* [REDACTED]

[REDACTED] All other comparisons between linaclotide dose (DR1, DR2, and IR) will be performed descriptively.

- b. For 6/12 Week APC+1 Responder rate, the protocol states:

*If the overall CMH statistic reaches statistical significance ( $\alpha = 0.05$ ), the tested formulation will be considered efficacious and the nature of the dose response will be explored among the individual linaclotide DR doses within the formulation.* [REDACTED]

The SAP clarifies statistical inference compares Placebo to each DR1 and DR2 doses only, regardless of the overall trend significance. All other treatment comparisons will be descriptive in nature.

- c. For each 6/12 Week and 9/12 Week responder endpoint defined in the protocol, a corresponding “Sustained Responder” was added. Each new ‘Sustained Responder’ parameter will be presented and analyzed as described in Sections [7.9.1.1](#) and [7.9.1.2](#)

- d. For the analyses of the 12-week Change from baseline, the protocol states:

[REDACTED]  
[REDACTED] All other comparisons between linaclotide dose (DR1, DR2, and IR) will be performed descriptively.

- e. For all responders in the “Other Efficacy Endpoint” section, the protocol states:

*All categorical responder parameters (e.g., Weekly CSBM +1 Responder) will be analyzed utilizing the same methods defined above for the key efficacy measure 6/12 Week APC +1 Responder.*

The SAP clarifies statistical inference compares Placebo to each DR1 and DR2 doses only. All other treatment comparisons will be descriptive in nature.

- f. For patients experiencing a TEAE coded as diarrhea, analyses of the number of days from first dose of study drug for the Treatment Period to the onset date of the first occurrence of treatment-emergent diarrhea during the Treatment Period listed in the SAP were not identified in the protocol.

- g. The endpoints and analyses of 6/12 and 9/12 Week Adequate Relief were not specified in the protocol.

## 9. DATA HANDLING CONVENTIONS

### 9.1 VISIT TIME WINDOWS FOR SAFETY ANALYSIS

Table 5 below presents the visits assigned for the safety analysis corresponding to the range of trial days (window) during which an actual visit may have occurred.

**Table 5. Visit Time Windows for Safety Analysis**

Derived Visit	Scheduled Test / Visit Day a	Window
Baseline	Day 1	Days $\leq 1$
Day 29 Visit	Day 29	Days [2, 43]
Day 57 Visit	Day 57	Days [44, 71]
Day 85 Visit	Day 85	Days [72, 99]
End of Trial b	Final or termination visit	

- a. Relative to the date of randomization; Day 1 = the day of randomization.
- b. "End of Trial" will be presented in analysis tables for safety parameters, including clinical laboratory and vital signs.

Test/Visit Day will be calculated as follows: test/visit date – date of randomization.

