**Figure 1. Overview of Study Design**

Note: there is no Day 0.

\*Applicable to a subset of patients

\*\*This visit represents the end of the study

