**Table 6. Analysis Time Windows for Efficacy Analysis**

Period	Analysis Week	Begins a	Ends a
Pretreatment (Baseline b )	Week -2	Day -14	Day -8
	Week -1	Day -7	Day 1 (time of randomization)
Treatment	Week 1	Day 1 (time of randomization)	Day 7
	Week 2	Day 8	Day 14
	Week 3	Day 15	Day 21
	Week 4	Day 22	Day 28
	Week 5	Day 29	Day 35
	Week 6	Day 36	Day 42
	Week 7	Day 43	Day 49
	Week 8	Day 50	Day 56
	Week 9	Day 57	Day 63
	Week 10	Day 64	Day 70
	Week 11	Day 71	Day 77
Week 12	Day 78	last dose day c (usually Day 85)	

Note: There is no Day 0 or Week 0. For eDiary assessments in which a patient is asked to report if an event occurred “yesterday” or “today” (e.g., a bowel movement or rescue medication use), these windows pertain to when the event occurred, not to when the event is reported. For example, if a patient reports in eDiary on Day 78 a bowel movement occurring “yesterday,” that bowel movement (and subsequent stool consistency and straining scores) would be included in Analysis Week 11, not Analysis Week 12.

- Relative to the date of randomization; Day 1 = the day of randomization. For the calculation of rates (e.g., stool frequency rates) in which the duration of a week or the overall period is calculated to the nearest hour, a day begins and ends at midnight.
- Baseline values for efficacy parameters will be derived from the daily eDiary and eCRF data collected in the Pretreatment Period, specifically the period from 14 days before randomization up to the time of randomization.
- For patients who fail to provide the date of last dose at the last visit, the last eDiary date will be used to impute the last dose date.

For the Treatment Period, diary day is calculated as diary date – date of randomization + 1. For the Pretreatment Period, diary day is calculated as diary date - date of randomization. However, the day of randomization is always trial Day 1. Patients will complete their diary entries once a day, with the exception of Day 1 of entry into the Treatment Period during which 2 diary data sets will be collected. On Day 1, daily questions will be entered before and after the randomization, whereas weekly questions will be entered before but not after randomization.

If a patient withdraws during the Treatment Period, the patient’s Treatment Period shall end on the day of the last dose. The affected Treatment Period week shall be shortened to the end of the

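### The safety visit-day formula in SAP 9.1 omits the +1, so randomization computes to Day 0 and results on four boundary days fall in the wrong Table 5 window

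*SAP*

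**What the plan says.** SAP 9.1, Table 5, assigns safety assessments to four day windows: Baseline (Day 1 or earlier), Day 29 (Days 2 to 43), Day 57 (Days 44 to 71) and Day 85 (Days 72 to 99). A fifth row, End of Trial, takes the final or termination visit and has no day window. Footnote a fixes the scale: "Relative to the date of randomization; Day 1 = the day of randomization". Directly below the table comes the formula: "Test/Visit Day will be calculated as follows: test/visit date", from which the date of randomization is subtracted, with no 1 added.

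Other parts of the SAP use the footnote's scale. The note to Figure 1 reads "Note: there is no Day 0", and the note to Table 6 reads "There is no Day 0 or Week 0". SAP 9.2 gives the diary counterpart: "For the Treatment Period, diary day is calculated as diary date – date of randomization + 1". It uses the plain difference only for the Pretreatment Period and adds that randomization always counts as trial Day 1. SAP 9.1 has neither the split nor that override.

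**The concern.** The footnote and the formula cannot both hold, because a date minus itself is 0. Two programmers, one following the footnote and the other the formula, would build different tables from the same data.

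The boundary days can be reached. Patients who withdraw early are asked to complete the end-of-treatment procedures even when out of window (SAP Table 2, footnote o), and those procedures include laboratory tests and vital signs. Such visits can fall on any day. The first dose is given in clinic at the Randomization Visit, so a result from the following day is post-dose, yet the literal formula places it in the window labelled Baseline.

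**Working it through.** **Inputs.** Windows, footnote a and formula: SAP Table 5. Comparison rule: SAP 9.2 (add 1 on or after randomization, plain difference before). Visit windows: Day 29±3, Day 57±3, Day 85+3 (SAP Table 2).

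**Step 1: the plan's own figure.** Footnote a requires randomization to be Day 1. The formula gives randomization date − randomization date = 0, so the stated figure is not reproduced. With +1 it is: 0 + 1 = 1.

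**Step 2: which scale the windows were built on.** Visits 28, 56 and 84 days after randomization compute to 28, 56 and 84 under the formula, and to 29, 57 and 85 with +1. The latter are the scheduled days in Table 5. The upper limits are 29 + 14 = 43, 57 + 14 = 71 and 85 + 14 = 99, so the windows fit the +1 scale.

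**Step 3: where the two rules disagree.** Both were applied to every date from 42 days before to 119 days after randomization. They assign different windows on exactly four dates:

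| Days after randomization | True day | Day by formula | Window by formula | Window with +1 |
|---|---|---|---|---|
| 1 | 2 | 1 | Baseline | Day 29 |
| 43 | 44 | 43 | Day 29 | Day 57 |
| 71 | 72 | 71 | Day 57 | Day 85 |
| 99 | 100 | 99 | Day 85 | none |

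**Step 4: scheduled visits.** True Days 26 to 32, 54 to 60 and 85 to 88 compute to 25 to 31, 53 to 59 and 84 to 87. Each stays in its own window.

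**Step 5: size.** Assume that 10% to 20% of 520 patients withdraw, evenly over 84 days, with the termination visit on the day of withdrawal.

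- Withdrawals: 0.10 × 520 = 52; 0.20 × 520 = 104.
- Day 2 only: 52 × 1/84 = 0.6; 104 × 1/84 = 1.2.
- Days 2, 44 and 72: 52 × 3/84 = 1.9; 104 × 3/84 = 3.7.
- Average per arm for the three days: 1.9/8 = 0.2; 3.7/8 = 0.5.

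Day 100 is outside this count because it lies beyond the 84 days. It would take a final visit well past the Day 85+3 window.

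**The case against.** The strongest case on the other side is that this is an editorial slip whose consequences the SAP already contains. Most of that stands.

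- **Baseline values.** A reader might infer that post-dose results contaminate the safety baseline. The documents do not support this. SAP 7.11 defines the laboratory and vital-sign baseline as the last non-missing value before the first dose, and SAP 9.5 repeats the rule for repeated assessments. A next-day result cannot become the baseline for change scores, whatever day number it receives.
- **Post-baseline summaries.** A reader might also infer that such results disappear from post-baseline reporting. They do not. The End of Trial row takes the termination visit regardless of day, SAP 9.5 uses the last non-missing post-baseline assessment for it, and all assessments are listed. What a Day 2 result loses is its place in the Day 29 column.
- **Safety signals.** SAP 9.5 uses all post-baseline assessments for PCS determination. Treatment-emergent adverse events are defined from the first and last dose (SAP 7.11.1), not from Table 5.
- **Adverse events behind Day 2 withdrawals.** It is tempting to suppose that patients who stop the day after the first dose often do so because of an adverse event. The Protocol introduction gives discontinuation rates for diarrhea from earlier trials but no timing, so nothing supports a cluster at Day 2.
- **Incomplete cure.** Adding 1 does not by itself keep post-dose data out of the Baseline window, because Day 1 or earlier still includes a post-dose result from the randomization day. This stands, and the fix has to cover it.

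The objection does not remove the contradiction. The formula is a complete sentence with no redaction, and it conflicts with its own table. For a Day 2 result, SAP 9.1 says Baseline while SAP 7.11 and 9.5 treat it as post-baseline.

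**Conclusion.** The formula in SAP 9.1 is wrong as written. It contradicts footnote a, both statements that there is no Day 0, and the parallel rule in SAP 9.2. The misassignment at true Days 2, 44, 72 and 100 follows from the documents alone and needs no assumption.

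The effect is limited to by-visit laboratory and vital-sign summaries for a few early-termination, unscheduled or well-out-of-window assessments. At Days 44 and 72 a result only moves to the preceding by-visit column. The patient counts in the working are orders of magnitude, since they rest on the assumed withdrawal rate, its even spread, and a termination visit on the day of withdrawal. Efficacy analyses are untouched because SAP 9.2 has its own day rule. This is a minor correction, worth making because a pre-specified plan should not leave the choice of day scale to the programmer.

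**What to change.** In SAP 9.1, replace the single formula with two cases, as SAP 9.2 does:

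- on or after the randomization date, day = assessment date minus randomization date, plus 1;
- before it, day = assessment date minus randomization date.

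Do not add 1 throughout, because that would turn the day before randomization into Day 0.

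Add one sentence stating that assignment to Baseline follows the pre-first-dose rule in SAP 7.11, so that post-dose results on Day 1 are excluded as well. Since the Day 29 window starts at Day 2, the same sentence should say where a post-dose Day 1 result is reported.

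The cost is a few lines of SAP text and the matching derivation in the safety datasets. No data collection, visit schedule or efficacy analysis changes, and I see no downside.

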### 9.2 VISIT TIME WINDOWS FOR EFFICACY ANALYSIS

Table 6 presents the analysis weeks assigned for the efficacy analysis of the patient diary data related to BM characteristics. These analysis weeks will be used in the calculations for all week-based parameters (e.g., SBM weekly frequency rate, BSFS weekly scores).

**Table 6. Analysis Time Windows for Efficacy Analysis**

Period	Analysis Week	Begins a	Ends a
Pretreatment (Baseline b )	Week -2	Day -14	Day -8
	Week -1	Day -7	Day 1 (time of randomization)
Treatment	Week 1	Day 1 (time of randomization)	Day 7
	Week 2	Day 8	Day 14
	Week 3	Day 15	Day 21
	Week 4	Day 22	Day 28
	Week 5	Day 29	Day 35
	Week 6	Day 36	Day 42
	Week 7	Day 43	Day 49
	Week 8	Day 50	Day 56
	Week 9	Day 57	Day 63
	Week 10	Day 64	Day 70
	Week 11	Day 71	Day 77
Week 12	Day 78	last dose day c (usually Day 85)	

Note: There is no Day 0 or Week 0. For eDiary assessments in which a patient is asked to report if an event occurred “yesterday” or “today” (e.g., a bowel movement or rescue medication use), these windows pertain to when the event occurred, not to when the event is reported. For example, if a patient reports in eDiary on Day 78 a bowel movement occurring “yesterday,” that bowel movement (and subsequent stool consistency and straining scores) would be included in Analysis Week 11, not Analysis Week 12.

- Relative to the date of randomization; Day 1 = the day of randomization. For the calculation of rates (e.g., stool frequency rates) in which the duration of a week or the overall period is calculated to the nearest hour, a day begins and ends at midnight.
- Baseline values for efficacy parameters will be derived from the daily eDiary and eCRF data collected in the Pretreatment Period, specifically the period from 14 days before randomization up to the time of randomization.
- For patients who fail to provide the date of last dose at the last visit, the last eDiary date will be used to impute the last dose date.

For the Treatment Period, diary day is calculated as diary date – date of randomization + 1. For the Pretreatment Period, diary day is calculated as diary date - date of randomization. However, the day of randomization is always trial Day 1. Patients will complete their diary entries once a day, with the exception of Day 1 of entry into the Treatment Period during which 2 diary data sets will be collected. On Day 1, daily questions will be entered before and after the randomization, whereas weekly questions will be entered before but not after randomization.

If a patient withdraws during the Treatment Period, the patient’s Treatment Period shall end on the day of the last dose. The affected Treatment Period week shall be shortened to the end of the

withdrawn patient’s Treatment Period, and all subsequent Treatment Period weeks will be missing for that patient.

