### **5.3.3 Removal of Patients From Therapy or Assessment**

A premature discontinuation will occur when a patient who signed the ICF ceases participation in the study, regardless of circumstances, before the completion of the protocol. Patients can prematurely discontinue or be prematurely discontinued by the investigator or sponsor from the study at any time for any reason including the following:

- Failure to meet Inclusion/Exclusion Criteria (Screen Failure)
- Adverse event (AE)
- Lack of efficacy
- Protocol violation
- Non-compliance with study drug
- Withdrawal of consent
- Lost to follow-up (every effort must be made to contact the patient; a certified letter must be sent)
- Study termination by Sponsor
- Pregnancy
- Other, such as administrative reasons

Patients who are randomized but do not complete the Treatment Period (withdraw consent or are discontinued before they have completed visits up to and including the Week 12/ End-of-Treatment Period (EOT) Visit, will be considered Treatment Period withdrawals and should complete the procedures required at the EOT Visit (even if out of window) at the time of their discontinuation. The reasons for premature discontinuation from the study will be documented on the study termination form of the eCRF. All data on the patient prior to discontinuation will be made available to Ironwood (or designee). Any patient who withdraws because of an AE will be followed until the AE resolves, stabilizes, or can be explained as being unrelated to study drug. The study centers should make a reasonable effort to follow pregnant patients until delivery or end of the pregnancy.

If a patient does not return for a scheduled termination visit (EOT Visit), the study center should contact the patient. Every effort is to be made to contact the patient, including sending a certified letter. In every case, the patient outcome, including lost to follow-up information, will be documented.

The investigator may allow a patient to stop taking study drug for up to three days should an intolerable AE occur. If the investigator believes that the patient is unable to resume dosing or requires a suspension of dosing on more than one occasion, the investigator should contact the Medical Monitor to discuss the patient's continued participation in the study.

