### ***Week 12/End-of-Treatment Period Visit (Visit 6)***

Patients who are randomized but do not complete the Treatment Period (withdraw consent or are discontinued before they have completed 12 weeks of treatment), will be considered Treatment Period withdrawals and should complete the procedures required at the EOT Visit (even if out of window). Any clinical findings obtained during the final examination or at premature discontinuation for any reason, including clinically significant laboratory abnormalities, will be followed until the condition returns to screening status, has resolved or stabilized, or can be explained as being unrelated to study drug.

The following procedures will be performed:

- Register visit in IWRS
- Physical examination (rectal, breast, and genitourinary examinations are optional at the discretion of the investigator)
- Body weight
- Seated vital signs
- Documentation of concomitant medicines
- Collection of blood for clinical laboratory determinations:
  - Clinical chemistry
  - CBC
- Serum pregnancy test
- Review of AEs
- Register visit in eDiary and eDiary compliance verification (study coordinator will verify the patient's compliance with the daily entry requirement); eDiary entry in the clinic, including the following assessments:
  - Daily BM-related Symptom-severity Assessments on an event-driven basis
  - Daily Abdominal Symptom-severity Assessments in a daily evening report
  - Use of Per-protocol Rescue Medicine or any other Laxatives, Suppositories, and Enemas on an event-driven basis
  - Weekly Patient Assessment of Constipation Severity
  - Weekly Patient Assessment of IBS Symptom Severity

- Weekly Patient Assessment of Adequate Relief
- SF-12v2 (self-administered by the patient; [Appendix VII](#))
- EQ-5D (self-administered by the patient; [Appendix VIII](#))
- SF-MPQ-2 (self-administered by the patient; [Appendix IX](#))
- Treatment Satisfaction Assessment (self-administered by the patient)
- Study drug accountability
- Register visit in IWRS (study coordinator will confirm in IWRS that the patient has completed participation in the study)

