## **7.6 EXTENT OF EXPOSURE**

Exposure to study drug for the Safety Population during the double-blind treatment period will be summarized by treatment group in terms of treatment duration and calculated as the number of days from the date of the first dose of double-blind study drug to the date of the last dose of double-blind study drug, inclusive. Overall treatment duration will also be categorized as 1 Day; >1 Day to  $\leq 7$  Days; >7 Days to  $\leq 30$  Days; >30 Day to  $\leq 90$  Days; and  $\geq 90$  Days.

Patient-years, defined as exposure to the study drug in years, will be summarized by treatment group for the Safety Population.

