## **9.6 MISSING DATE OF THE LAST DOSE OF STUDY DRUG**

When the date of the last dose of double-blind study drug is missing for a patient in the Safety Population, all efforts should be made to obtain the date from the Investigator. If after all efforts are made it is still missing, the last eDiary entry will be used as the last dose date.

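### For a non-completer with no last-dose date, imputing the last eDiary date normally picks up the EOT-visit entry, so off-drug days can count as treatment

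*SAP*

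**What the plan says.** **The imputation rule.** Table 6 in SAP 9.2 defines the efficacy analysis weeks. Its footnote c says that where patients "fail to provide the date of last dose at the last visit, the last eDiary date will be used to impute the last dose date". SAP 9.6 has the same rule for the Safety Population, as a fallback: first, "all efforts should be made to obtain the date from the Investigator"; if that fails, "the last eDiary entry will be used as the last dose date".

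**Early withdrawers and the diary.** Under Visit 6 in Protocol 5.5.1, patients who do not complete treatment "should complete the procedures required at the EOT Visit (even if out of window"). The procedures for that visit include "eDiary entry in the clinic, including the following assessments". Protocol 5.3.3 adds the intended timing: "even if out of window) at the time of their discontinuation". It sets no maximum interval between the last dose and the visit.

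**What depends on the date.** SAP 9.2 says that a withdrawn patient's "Treatment Period shall end on the day of the last dose"; later weeks are missing. Exposure (SAP 7.6) is the "number of days from the date of the first dose of double-blind study drug to the date of the last dose". The compliance denominator (SAP 7.5) is twice the number of days in that interval. An AE starting more than one day after the last dose is not a TEAE (SAP 7.11.1).

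**Diary gaps.** Under SAP 9.4.2 a day without reports is treated as a day without bowel movements or rescue medicine. Under SAP 9.4.3.1 the length of an analysis week is not shortened for missed reports.

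**The concern.** The SAP intends a withdrawer's data to be cut off at the last dose. The fallback can defeat that cut-off. A patient who stopped drug, came to EOT some days later and could not date the last dose will have made an eDiary entry at that same visit. The last eDiary date is then the visit date, whatever day dosing ended. Neither document excludes the EOT entry or checks the imputed date against the unit counts, which are collected anyway.

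The patient need not have kept the diary going. If diary and drug stopped together, one late EOT entry extends the Treatment Period over the silent interval, and the gap rule fills it with zero bowel movements. Weekly CSBM frequency is a key parameter, so a week that should be missing becomes an observed week at rate 0. Weekly pain is less exposed: it averages non-missing scores, so it changes only through entries made off drug. Exposure, patient-years, compliance and TEAE attribution for that patient are wrong in either case.

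**Working it through.** **1. The plan's own power figure, used as the yardstick in step 4.** Inputs from SAP 4: means −1.196 (placebo), −1.586 (30 µg), −1.975 (100 µg), −1.975 (300 µg); SD 1.73; 65 per arm; contrast −3, −1, 1, 3.

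- L = 3.588 + 1.586 − 1.975 − 5.925 = −2.726
- SE = 1.73 × √(20/65) = 0.9596
- Power = Φ(2.726/0.9596 − 1.96) = 81.1%, against the stated 81%. Reproduced.

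**2. One patient, by day counting.** Assumptions, because the documents give no dates: 20 doses taken on Days 1–20; drug and diary both stop on Day 20; last-dose date still missing after query; EOT entry *g* days later; 3 CSBMs/week while on drug and none reported at the EOT entry.

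- Exposure = 20 + g
- Compliance = (2 × 20)/(2 × (20 + g))
- TEAE window closes on Day 20 + g + 1
- Treatment Period CSBM rate (SAP 9.4.3.3) = 3 × 20/(20 + g)

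| g (days) | Exposure | Compliance | TEAE window closes | Off-drug days analysed as treatment | CSBMs/week, whole period |
|---|---|---|---|---|---|
| 0 | 20 | 100% | Day 21 | none | 3.00 |
| 1 | 21 | 95.2% | Day 22 | Day 21 | 2.86 |
| 3 | 23 | 87.0% | Day 24 | Day 21, 2 days of Week 4 | 2.61 |
| 7 | 27 | 74.1% | Day 28 | Day 21, 6 days of Week 4 | 2.22 |
| 14 | 34 | 58.8% | Day 35 | Day 21, all of Week 4, 6 days of Week 5 | 1.76 |

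At g = 14 exposure is overstated by 34/20 − 1 = 70%, and the patient moves from the SAP 7.6 category ending at 30 days to the next one.

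**3. The weekly CSBM value.** At g = 14, Week 4 is Days 22–28. It has its full 168 hours and no reports, so the SAP 9.4.3.2 formula gives 168 × 0/168 = 0. With the true date, Week 4 would be missing. If the other 64 patients in the arm averaged 3 per week, this one zero would lower the arm's Week 4 mean by 3 − (64 × 3)/65 = 0.05.

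**4. The trial as a whole.** Assume that a share *f* of patients is affected and each loses a share *s* of the effect. Power is then Φ(2.841 × (1 − f × s) − 1.96).

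- f = 1%, s = 10%: 81.0%
- f = 5%, s = 30%: 79.9%

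These shares mean about 5 to 26 of 520 patients. The calculation is for pain, with the SD held fixed; the documents give no planning values for CSBM.

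**The case against.** The case against has several parts, and most of them stand as limits.

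- **The rule is a last resort.** SAP 9.6 requires the investigator query first. AE withdrawers should also be well documented, because Protocol 5.5.3.2.1 requires the action taken with study drug to be recorded. Few dates should remain missing.
- **The gap may be zero.** The ordinary EOT Visit cannot take place before Day 85 (Protocol 5.5.1), so the out-of-window wording mainly permits an early visit, and Protocol 5.3.3 places it at discontinuation. A 14-day gap is not the planned course. Still, no limit is set, and Protocol 5.3.3 allows dosing to be suspended for up to three days, which could precede a withdrawal.
- **Responder counts are largely protected.** SAP 7.9 requires 4 complete evening reports in a week, so a silent off-drug week cannot become a responder week; that takes continued diary use off drug. The multiple-imputation sensitivity analysis (SAP 7.9.1.2) also sets weeks with fewer than 4 complete evening diaries to missing. The main observed-case CSBM model has no such rule.
- **For TEAEs the current rule is the inclusive one.** That is true, but it does not help exposure, compliance or CSBM frequency.

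A reader might infer that the imputed date is always the visit date. It is not: Protocol 5.3.3 foresees patients who never return. They have no in-clinic entry, and their last eDiary date may fall before or after the true last dose.

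A reader might also infer that the error concentrates in the higher DR doses, because diarrhea led to discontinuation in 5.3% on linaclotide and 0.4% on placebo in the earlier trials (Protocol 3). Those are figures for the IR formulation at 290 µg, and the protocol says that frequency and severity on DR are still to be determined. The patients at issue are those whose date survives a query, not all withdrawers. The documents do not show how they fall across arms.

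**Conclusion.** The point holds as a minor data-handling defect. For a non-completer whose last-dose date is still missing after query and who attends EOT after stopping drug, the stated rule normally returns the EOT date. Off-drug days then enter the weekly CSBM analysis, exposure, the compliance denominator and the TEAE window.

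For one patient the error can be large: up to 14 extra days and 58.8% compliance in the assumed example, but only one day and 95.2% when the gap is a single day. For the trial it is likely negligible: under the assumed shares, trend power for pain stays between 79.9% and 81.0%. The number of missing dates and the gap are not in the documents, so both sizes are illustrations. A reading that the dose-response conclusion is at risk is not supported.

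**What to change.** In SAP 9.2 footnote c and in SAP 9.6:

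1. For patients who did not complete treatment and whose date is still missing after query, disregard the eDiary entry made at the EOT Visit and impute the date of the last eDiary entry before it.
2. Use drug accountability only as a consistency floor: the imputed date is not earlier than first-dose date + units taken − 1, and not later than the EOT Visit.
3. Keep the present rule for completers.
4. Report the number of imputed last-dose dates by arm.

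In the Day 20/Day 34 example this gives Day 20 from the diary and 1 + 20 − 1 = Day 20 from the floor, so compliance returns to 40/40 = 100% and Week 4 is missing.

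Accountability should not enter as the earliest of several candidate dates. At one dose a day, first dose + units taken − 1 is the earliest possible last-dose day. A patient who stopped on Day 60 after 48 doses (48/60 = 80% compliance) would be dated to Day 48 with 48/48 = 100% by construction, and 12 real treatment days would be lost.

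The cost is a sentence in two places, about a line of derivation code and one table row. The TEAE window becomes slightly less inclusive. The last entry before EOT can still miss the true last dose by some days: a patient who kept the diary to Day 33 in the example would be dated to Day 33, so the change mainly helps where diary and drug stopped together.
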